### **8.1.1. Sample Size**

To determine a recommended schedule and dose range of LY2875358 in combination with ramucirumab that may be safely administered to patients with advanced and/or metastatic cancer, an adequate patient sample size is required. A sufficient sample size will allow for an accurate evaluation of the relationship between exposure and toxicity, as well as an evaluation of the relationship between exposure and pharmacological effects using descriptive statistics and appropriate modeling techniques, if data warrant. This sample size is estimated to be a total of approximately 70 patients (6-12 [Part A] + 60 [Part B]).

For Part A, following a 3+3 dose escalation scheme, the sample size calculation assumes that cohorts will include 3 to 6 patients. If 2 cohorts for the intended 2 dose levels for LY2875358 (ie, 750 and 2000 mg) are needed to determine a recommended dose range for LY2875358 in combination with ramucirumab, then approximately 6-12 patients will be enrolled in Part A. To ensure accurate evaluation of safety, tolerability, or PK/PD biomarkers, additional patients may

be enrolled during Part A if deemed appropriate based on agreement between the investigators and the sponsor.

For Part B, the sample size of approximately 15 patients per expansion cohort was selected to allow adequate confirmation of safety and tolerability of LY2875358 in combination with ramucirumab and to identify evidence of preliminary clinical activity worthy of further investigation in Phase 2, analogous to the first stage of a Simon's two-stage design. If the true clinical RR according to RECIST for the combination of ramucirumab and LY2875358 in 1 of the tumor types selected is 10%, then there is a 79% chance of observing at least 1 patient with a clinical response, which might warrant further study of the regimen. On the other hand, if the true RR is close to the RR of ramucirumab monotherapy (for example, 3% in REGARD), then there is a 36.7% chance of incorrectly concluding that the regimen merits further study. In addition, variable response to treatment due to genetic variation can be measured based on patients' post-progression tumor samples. It is assumed that 50% of the study population is expected to be biomarker positive, and the true response rates are 40% and 3% in the biomarker positive and biomarker negative group respectively. Since the observed number of biomarker positive patients can vary, the sample size of 15 would give us a weighted average power of 40% (i.e. each power is weighted by its associated probability of observed number of biomarker positive patients) based on 2-sided type 1 error rate of 20% to detect statistically significant dependence between biomarker status and clinical response, suggesting the potential clinical utility of the biomarker for identifying the most appropriate target population.

In case of significant clinical activity in any of the tumor-specific expansion cohorts, further patients may be added to enroll up to approximately 45 patients per cohort to further characterize the safety and explore preliminary clinical activity of LY2875358 in combination with a fixed regimen of ramucirumab treatment, if deemed appropriate after discussion and mutual agreement between the investigators and the sponsor. A sample size of 45 would give us a weighted average power of 83% based on 2-sided type 1 error rate of 5% to detect the significant dependence between biomarker status and clinical response as above. The criterion of significant clinical activity may vary based on tumor-specific response rates or landmark disease control. [Table JTBF.1](#) summarizes the parameters of Simon's optimal two-stage design for each cohort. The uninteresting RR of Gastric/GEJ, HCC, RCC are referenced from previous trials JVBD, JVBD and JVBP. The uninteresting RR of NSCLC is based on the RR in the second-line docetaxel arm (Scagliotti et al. 2011). Alternatively, disease control may be considered in order to proceed with enrollment up to 45 patients per cohort if deemed appropriate. [Table JTBF.2](#) summarizes landmark disease control and landmark disease control considered of interest to enroll up 45 patients per cohort. Such decisions will be documented in writing following discussions between the investigators and the sponsor, and a written notification will be sent to the IRB prior to enrollment of further patients.

**Table JTBF.1. Simon's Optimal Two-stage Design Parameters for Each Cohort**

Tumor Type	Uninteresting RR	Favorable RR	1-sided type 1 error rate	Power	$n_1$	n	$r_1$	r
Gastric/GEJ	3%	10%	0.15	0.7	14	45	1	3
HCC	10%	22%	0.1	0.75	14	42	2	7
RCC	5%	12%	0.15	0.7	13	45	1	4
NSCLC	8.5%	22%	0.1	0.8	14	41	2	6

Abbreviations: GEJ = gastroesophageal junction; HCC = hepatocellular carcinoma;  $n_1$  = number of patients enrolled in the first stage; n = total number of patients enrolled; NSCLC = non-small cell lung cancer;  $r_1$  = number of responses required to proceed to the second stage; r = total number of responses required for further investigation of the drug; RCC = renal cell carcinoma; RR = response rate.

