6.16. Interim Analyses and Data Monitoring

An interim analysis will be performed after completion of Part A. Data will be reviewed on a cohort-by-cohort basis during the study until the MTD is determined. The purpose of these cohort-by-cohort reviews is to evaluate the safety data at each dose level and to determine if a DLT has been observed that would suggest MTD has been met or exceeded.

For Part B, both safety and efficacy data will be assessed. Interim analyses will be conducted after approximately 15 patients have completed 3 cycles in Parts B1,B2 and B4 (gastric, hepatocellular cancers and non-small cell lung cancer) and 6 cycles in Part B3 (renal cell cancer).

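### Table JTBF.1's Simon error rates hold only at its tabled sizes; with looks at about 15 and expansion to about 45, HCC and NSCLC error is 10.2% to 13.1% against a stated 10%, and the disease-control route makes the stage-1 stop non-binding

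*Protocol*

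**What the plan says.** Protocol Table JTBF.1 gives one Simon optimal two-stage design per cohort. The columns are null rate, favourable rate, one-sided error, power, n1, n, r1 and r. The HCC row reads "HCC 10% 22% 0.1 0.75 14 42 2 7", which means a look at 14 patients and a total of 42. The NSCLC row reads "NSCLC 8.5% 22% 0.1 0.8 14 41 2 6", which means a look at 14 and a total of 41. The other two cohorts already end at 45: gastric looks at 14 patients with r1 = 1 and r = 3 (null 3%, favourable 10%, error 0.15, power 0.7), and RCC looks at 13 with r1 = 1 and r = 4 (null 5%, favourable 12%, error 0.15, power 0.7).

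The footnote defines n1 as the "number of patients enrolled in the first stage", and r1 and r as the responses required to continue and to justify further investigation.

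The conduct text uses other sizes. Protocol 8.1.1 plans about 15 patients per cohort and calls this analogous to a Simon first stage. Protocol 12.8 times the Part B looks from the 15th patient. SAP 6.16 says: "Interim analyses will be conducted after approximately 15 patients have completed 3 cycles in Parts B1,B2 and B4". On expansion, Protocol 8.1.1 says "further patients may be added to enroll up to approximately 45 patients per cohort", with the same ceiling for all four tumour types. It then opens a second route: "Alternatively, disease control may be considered in order to proceed with enrollment up to 45 patients per cohort if deemed appropriate". Table JTBF.2 lists the landmarks of interest: 60% against 40% for gastric, 75% against 50% for the other three.

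SAP 5.2 repeats the scheme, but its HCC row (Table JTBF.5.2) has r1 = 1 where the protocol has 2.

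**The concern.** A Simon design's error rate belongs to one set of n1, n, r1 and r. If more patients are enrolled and r does not move, r responses become easier to reach under the uninteresting rate. If a cohort that misses r1 can still continue, the early stop that holds the error down is no longer guaranteed. Neither document re-derives r1 or r for 15/45, restricts them to the first n1 and first n patients, or gives error rates for the disease-control route. At stake is whether the stated error rates describe the decision that r is meant to support, namely whether a regimen merits further investigation in a given tumour type.

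**Working it through.** **Inputs.** Null rate p0, favourable rate p1, n1, n, r1 and r come from Table JTBF.1. The sizes 15 and 45 come from Protocol 8.1.1 and 12.8 and SAP 6.16. Following the footnote, r1 and r are read as counts required (at least).

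**Formula.** P(success) = sum over x ≥ r1 of P(X1 = x) × P(X2 ≥ r − x), with X1 ~ Bin(n1, p) and X2 ~ Bin(n − n1, p). Error uses p0 and power uses p1.

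**Step 1: reproduce the table.** At the tabled sizes, error/power is:

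- gastric 0.110/0.701
- HCC 0.098/0.761
- RCC 0.149/0.701
- NSCLC 0.097/0.806

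All four meet their stated limits. A search for the optimal design at each stated error and power returns the same four rows, so the reading of r1 and r is right.

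**Step 2: 15 then 45, r1 and r unchanged, stop kept.** The last term in each sum is P(X1 ≥ r).

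- HCC (p0 = 0.10, r1 = 2, r = 7): 0.2669×0.1755 + 0.1285×0.3526 + 0.0428×0.5887 + 0.0105×0.8163 + 0.0019×0.9576 + 0.0003 = 0.128
- NSCLC (0.085, 2, 6): 0.2391×0.2486 + 0.0962×0.4751 + 0.0268×0.7364 + 0.0055×0.9304 + 0.0010 = 0.131
- RCC (0.05, 1, 4): 0.3658×0.1878 + 0.1348×0.4465 + 0.0307×0.7854 + 0.0055 = 0.158
- Gastric (0.03, 1, 3): 0.2938×0.2269 + 0.0636×0.5990 + 0.0094 = 0.114

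**Step 3: 15 then the tabled n.** HCC (15/42) and NSCLC (15/41) are each 0.102. Gastric and RCC already have n = 45, so they stay as in step 2.

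| Cohort | Stated error | As tabled | 15 / tabled n | 15/45 | Power, tabled → 15/45 |
|---|---|---|---|---|---|
| Gastric | 15% | 11.0% | 11.4% | 11.4% | 70.1% → 72.0% |
| HCC | 10% | 9.8% | 10.2% | 12.8% | 76.1% → 81.3% |
| RCC | 15% | 14.9% | 15.8% | 15.8% | 70.1% → 73.2% |
| NSCLC | 10% | 9.7% | 10.2% | 13.1% | 80.6% → 85.1% |

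For HCC and NSCLC almost all of the rise comes from a final size of 45 rather than 42 or 41. Moving stage 1 from 14 to 15 adds about half a point.

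**Step 4: the disease-control route at 45 patients.** Let q be the chance that a cohort missing r1 is expanded anyway. Then error = (15/45 value) + q × P(X1 < r1 and total ≥ r):

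- gastric 0.114 + 0.038q
- HCC 0.128 + 0.030q
- RCC 0.158 + 0.028q
- NSCLC 0.131 + 0.049q

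At q = 1 this is P(X ≥ r | 45, p0): 15.2% gastric, 15.9% HCC, 18.7% RCC, 18.0% NSCLC.

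Suppose instead that the landmark is applied strictly to 15 patients, with no true landmark effect and independence from response (assumptions). Then q = P(at least 12 of 15 | 0.50) = 0.018 for HCC, RCC and NSCLC, and P(at least 9 of 15 | 0.40) = 0.095 for gastric. The added error is at most 0.049 × 0.018 = 0.001 in the first three and 0.038 × 0.095 = 0.004 in gastric.

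**Step 5: the SAP's HCC row.** With r1 = 1 read as required, HCC error is 11.7% at 14/42 and 15.3% at 15/45.

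**The case against.** The table contains no arithmetic error, and its sizes can be read as fitting the rounded text: 41 to 45 lies under a ceiling of about 45, and 13 or 14 is close to about 15. No sentence says that r = 7 or r = 6 is to be applied to 45 patients. On the narrow reading, HCC and NSCLC sit at 10.2%, practically the stated figure. RCC exceeds its limit by less than a point, and gastric stays inside.

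The consequence is also limited. Protocol 12.1 and SAP 6.1 call the analyses descriptive. Protocol 12.6 says the study was not designed for comparative efficacy. SAP 6.12 plans an ORR with a Clopper-Pearson interval and does not use r. An HCC result of 7/45 would be reported with a lower limit of about 6.5%, below the 10% null. Protocol 8.1.1 openly accepts a 36.7% chance of a false signal from a single response in 15 at a 3% rate, and treats expansion as a documented judgement.

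Most of this stands. It rules out calling the table wrong or the Part B analysis invalid. It does not remove the gap: ORR is the Part B co-primary objective, r is defined as the threshold for further investigation, and the plan chose to state error rates for it. For HCC and NSCLC, every final size from the tabled n to 45 gives an error above 10% once the look is at 15.

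**Conclusion.** The point holds as a mismatch between table and text, of moderate severity. With the stop kept and r1 and r unchanged, error is 10.2% to 12.8% for HCC and 10.2% to 13.1% for NSCLC (stated 10%), and 15.8% for RCC (stated 15%). Gastric meets its limit at 11.4%. Power rises in every cohort, so only type I error is affected.

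A reader might infer three stronger things that the documents do not support:

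- **That 13% is simply the error rate of the trial as run.** It is the top of a range, and it assumes r is applied to 45 patients, which neither document states.
- **That the disease-control route produces the 13%.** That figure has the stop fully in force. The route is a separate matter: its ceiling of 15.2/15.9/18.7/18.0% (gastric/HCC/RCC/NSCLC) needs every cohort that misses r1 to be expanded while its response rate is null. Strict use of the landmarks adds little, but the discretionary wording leaves q unspecified.
- **That the co-primary conclusion fails.** The planned ORR analysis is estimation, and r is a go/no-go threshold beside it.

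**What to change.** 1. Reconcile HCC r1 first (protocol 2, SAP 1). Only r1 = 2, read as required, keeps the tabled 14/42 design within 10%.

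2. Then choose one of two routes, in Protocol 8.1.1 and SAP 5.2:
   - State that r1 and r are judged on the first n1 and first n patients in the table, with later patients used only for estimation. The tabled error rates then stand while the stop is kept.
   - Restate the design at 15/45:
     - NSCLC r = 7: error 6.7%, power 81.3%.
     - HCC r = 8: 6.5%/74.5% with r1 = 2, which falls just short of the stated 0.75, so power is restated as 0.74; or 7.4%/79.6% with r1 = 1.
     - RCC keeps r = 4 with error restated as 0.16.
     - Gastric is unchanged.

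3. Add one sentence: a cohort expanded on disease control with fewer than r1 responses has its ORR reported descriptively, without the r rule.

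The cost is table and wording edits, best made before any Part B expansion decision. Under the 15/45 route, HCC and NSCLC each need one more response, and RCC carries a slightly less favourable stated error rate.

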**Table JTBF.2. Previously Observed Landmark Disease Control for Each Cohort**

Tumor Type	Observed Landmark	Landmark of Interest
Gastric/GEJ	12-weeks PFS 40%	60%
HCC	4-mos PFS 50%	75%
RCC	7.1-mos PFS 50%	75%
NSCLC	3-mos PFS 50%	75%

Abbreviations: GEJ = gastroesophageal junction; HCC = hepatocellular carcinoma; mos = months; NSCLC = non-small cell lung cancer; PFS = progression-free survival; RCC = renal cell carcinoma

### 8.1.2. Rationale for Selection of Dose

In this study, ramucirumab will be administered at a fixed regimen of 8 mg/kg in combination with LY2875358 at a dose range of 750-2000 mg, both administered Q2W.

The ramucirumab dose and schedule of 8 mg/kg Q2W IV infusion is the same as those for which safety and clinical efficacy have been demonstrated in Phase 2 and/or Phase 3 studies in gastric and GEJ adenocarcinoma, hepatocellular carcinoma, and renal cell cancer patients.

The LY2875358 dose range of 750-2000 mg administered as an Q2W IV infusion combination with ramucirumab was selected based on the safety and PK profile established for LY2875358 monotherapy in the Phase 1 Study JTBA and in preclinical in vivo efficacy studies. A Target-Mediated Drug Disposition (TMDD) model adequately fit the human PK data from the Study JTBA dose escalation and was used to simulate the dose range of 700-2000 mg Q2W. In this dose range, non-receptor-mediated clearance predominates, suggesting that receptors (MET) are saturated. Also, based on the simulations of LY2875358 PK of 750 mg Q2W, 100% of the population is predicted to have a minimum concentration at steady state ( $C_{ss,min}$ )  $\geq 50 \mu\text{g/mL}$ , which is the  $C_{ss,min}$  associated with maximal tumor growth inhibition in the ligand-independent xenograft model MKN45. Furthermore, based on in vivo target inhibition studies, MET

inhibition at the level of the tumor would be maximized at a dose of 750 mg Q2W. In addition, PRs were observed in Study JTBA in the 700- to 2000-mg dose range. Two patients who received doses of 700 mg and 2000 mg as monotherapy achieved a PR (data on file). Two patients who received LY2875358 in combination with erlotinib achieved a PR, 1 each at doses of 700 mg and 2000 mg. Therefore, LY2875358 exposures achieved by 700-2000 mg Q2W are expected to be sufficient to prevent HGF binding and signaling, reduce expression of MET, and inhibit MET-driven growth of solid tumors.

Patients enrolled in this study will be closely monitored for safety and tolerability of the combination of ramucirumab and LY2875358. Dose escalation following a 3+3 dose escalation scheme in Part A will be only allowed after evaluation of all safety data. In addition, available PK/PD results will be reviewed prior to dose escalation.

### **8.1.3. Study Completion and End of Trial**

This study will be considered complete (that is, the scientific evaluation will be complete [study completion]) following the final analysis. “End of trial” refers to the date of the last visit or last scheduled procedure for the last patient.

## **8.2. Discontinuations**

### **8.2.1. Discontinuation of Patients**

The criteria for enrollment must be followed explicitly. If the investigator site identifies a patient who did not meet enrollment criteria and who was inadvertently enrolled, the sponsor must be notified. If the sponsor identifies a patient who did not meet enrollment criteria and who was inadvertently enrolled, the investigator site will be notified. A discussion must occur between the sponsor CRP/clinical research scientist (CRS) and the investigator to determine whether the patient may continue in the study, with or without investigational product. Inadvertently enrolled patients may be maintained in the study and on investigational product when the Lilly CRP/CRS agrees with the investigator that it is medically appropriate for that patient. The patient may not continue in the study with or without investigational product if the Lilly CRP/CRS does not agree with the investigator’s determination that it is medically appropriate for the patient to continue. The investigator must obtain documented approval from the Lilly CRP/CRS to allow the inadvertently enrolled patient to continue in the study with or without investigational product.

Patients will be discontinued from the study drug(s) in the following circumstances:

- The patient has evidence of progressive disease.
  - NOTE: In select cases, after discussion with the sponsor, treatment beyond progression may be permissible if the patient is thought to be deriving ongoing benefit from the study therapy. For instance, local therapies, such as radiation treatment to control isolated areas of CNS progression, may be permissible provided study drugs are held on the days of local therapy. Additional systemic therapy, however, is not allowed. This option is contingent upon study drug

availability. Patients may continue until they fulfill another one of the criteria for study discontinuation.

- The patient experiences unacceptable toxicity that is deemed related to study drug(s) (eg, a persistent moderate toxicity that is intolerable to the patient).
- The patient experiences a Grade 3 or 4 infusion-related reaction related to study drug(s). The patient should be permanently discontinued from ramucirumab for any of the following events (see Section 9.2.3.2):
  - Grade 4 hypertension or persistent/recurrent hypertension
  - Grade 4 proteinuria or persistent/recurrent proteinuria  $>3$  g/24 hours
  - Grade 3 or 4 ATE

  - If the patient, for any reason, requires treatment with another therapeutic agent that has been demonstrated to be effective for treatment of the study indication, discontinuation from the study drug(s) must occur prior to introduction of the other agent
- Patient Decision
  - The patient requests to be discontinued from the study or study drug
- Sponsor Decision
  - Lilly stops the study or stops the patient's participation in the study for medical, safety, regulatory, or other reasons consistent with applicable laws, regulations, and GCP
- The patient is significantly noncompliant with study procedures and/or treatment (Section [9.6](#)).

The reason for and date of discontinuation will be collected for all patients. The Date of Discontinuation (for any of the above reasons) from study treatment is to be reported on the electronic case report form (eCRF). Patients who discontinue will have follow-up procedures performed as shown in the Study Schedule ([Attachment 1](#)).

### ***8.2.2. Discontinuation of Study Sites***

Study site participation may be discontinued if Lilly, the investigator, or the ethical review board (ERB) of the study site judges it necessary for any scientific, medical, safety, regulatory, ethical, or other reasons consistent with applicable laws, regulations, and GCP.

### ***8.2.3. Discontinuation of the Study***

The study will be discontinued if Lilly, while considering the rights, safety, and well-being of the patient(s), judges it necessary for any scientific, medical, safety, regulatory, ethical, or other reasons consistent with applicable laws, regulations, and GCP.

## 9. Treatment

### 9.1. Materials and Supplies

#### 9.1.1. *Ramucirumab*

Ramucirumab, provided by Lilly, is a sterile, preservative-free solution for infusion formulated in an aqueous solution at a concentration of 10 mg/mL (500 mg/50 mL vial). The buffer contains 10 mM histidine, 75 mM sodium chloride, 133 mM glycine, and 0.01% polysorbate 80. Ramucirumab is a clear or slightly opalescent and colorless or pale yellow liquid without visible particles. The pH is 6.0. The osmolality is 285 mmol/kg.

Ramucirumab must be stored under refrigeration at 2°C to 8°C with protection from direct light. DO NOT FREEZE AND/OR SHAKE RAMUCIRUMAB. Stability studies have demonstrated that the drug product can withstand transient excursion to room temperature without adverse effect; however, storage at this temperature is not recommended.

#### 9.1.2. *LY2875358*

LY2875358 will be provided by Lilly as investigational product. LY2875358 for injection is a lyophilized product supplied in glass vials containing 75 mg of LY2875358. This product is reconstituted with 3.2 mL of sterile water for injection, resulting in 25 mg/mL of LY2875358. The reconstituted formulation is stable for up to 6 hours at room temperature. For further instructions, please refer to the pharmacy binder.

LY2875358 should be stored within the temperature range stated on the label.

Clinical study materials will be labeled according to the country's regulatory requirements.

### 9.2. Study Drug Administration

The investigator or designee is responsible for:

- explaining the correct use of the investigational agents and planned duration of each individual's treatment to the site personnel
- verifying that instructions are followed properly
- maintaining accurate records of study drug dispensation, destruction, and collection, and
- returning or destroying all unused medication to Lilly or its designee at the end of the study.

Patients will be instructed to contact the investigator as soon as possible if they have a complaint or problem with the study drugs so that the situation can be assessed.

Eligible patients will receive 2 cycles of study drugs, unless 1 or more of the criteria for discontinuation (per Section 8.2.1) are met. Patients who have completed 2 cycles and are receiving clinical benefit may remain on study provided they have not met any criteria for study

discontinuation (per Section 8.2.1). If tolerated, ramucirumab and LY2875358 infusions should be administered on the same day to keep the schedule of both study drugs synchronized.

